9.4. Data Sources

This study will be conducted using Komodo Health's Healthcare Map™. The data source is a healthcare technology firm owning, linking, and integrating both open and closed-claims databases from over 150 public and private payers/insurers as well as clearinghouses across the US. The database linkage uses Datavant's encryption and tokenization technology. The data covers more than 330 million individuals including both current (alive) and historical (deceased during the time of study) patients. The database is closely aligned with the National Health Interview Survey population in terms of geography and demographics. This source of insurance claims data encompasses comprehensive, longitudinal records detailing medical procedures, diagnoses, treatments, and associated costs within the healthcare system, as well as patient characteristics and outcomes such as race/ethnicity, zip code, and all-cause mortality records. In this iteration of the Komodo Healthcare Map, only patients with at least one ICD diagnosis code for MM are included in the database.

Mortality records in the data source are obtained from government public records, private claims, and obituaries. For Health Insurance Portability and Accountability Act compliance reasons, mortality is truncated to the year/month of death (YYYY-MM-01). Multiple sources of data are then evaluated, and death dates within 30 days of each other are deduplicated. If multiple sources report different death dates for the same person, then the earlier date is taken.

In order to impute costs, Komodo Heath utilizes the data provided to them by their data sources as well as from as well as publicly available Centers for Medicare & Medicaid Services Medicare fee-for-service pricing tools and methodologies.

This study involved secondary research that utilized de-identified data licensed from a third party, Komodo, in compliance with 45 Code of Federal Regulations 164.514(a)-(c).

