9.7.2. Treatment Exposure Outcomes

Treatment exposure outcomes include RAI and time between administrations. The assessment periods shown in Table 4 are based on the elranatamab label instructions and will be used to measure treatment and dosing-related outcomes for patients receiving elranatamab.¹⁸ These periods are also provided in Figure 2.

[figure not shown]
Table 4. Dosing Schedule and Expected Administrations and Vial Size of Elranatamab

Dosing Schedule	Time Period	Expected Administrations	Vial Size

[figure not shown]
Step-Up	Index date - Day 8	3 during Step-Up	44mg/1.1mL
Maintenance Period 1	Day 9 - Day 168	1 per week	76mg/1.9mL
Maintenance Period 2	Day 169 – Censor	1 every two weeks	76mg/1.9mL

Figure 2. Dosing Schedule for Elranatamab and Teclistamab

Elranatamab label instructions

Teclistamab label instructions

The assessment periods shown in Table 5 are based on the teclistamab label instructions and will be used to measure treatment and dosing-related outcomes for patients receiving teclistamab.¹⁹ These periods are also provided in Figure 2.

Table 5. Dosing Schedule and Expected Administrations and Vial Size of Teclistamab

Dosing Schedule	Time Period	Expected Administrations	Vial Size
Step-Up	Index date - Day 7	3	30 mg/3mL
Maintenance Period	Day 8 - Censor	1 per week	153 mg/1.7mL

Dosing outcomes (reported vial size, average time between claims, and frequency of claims) will be assessed during the above time periods regardless of whether the number of administrations during the period matches the number indicated on the label instructions. Duration on treatment will be measured from the first administration to the last administration of the index drug.

Patients will be censored at the earliest of death, next treatment (CAR-T, BsABs, bendamustine, or belantamab), the end of observability, or the latest data at the time of the specified analysis.

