9.7.4. Time to Discontinuation

TTD will be assessed as the time in months (1 month = 30.4375 days) using Kaplan-Meier methods. Median time-to-event will be reported along with the IQR. The 95% CIs for the median time-to-event will be calculated using log-log transformation. Results will be depicted graphically by Kaplan-Meier curves.

Patients who do not have a recorded discontinuation event or death will be censored on the earliest of the end of continuous closed-claim coverage or the end of data.

The percentage of patients who reached the outcome, as well as the percentage of censored patients, will be reported.

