9.7.5. Healthcare Resource Utilization and Cost

All-cause HCRU and MM-related HCRU (ie, HCRU with a diagnosis code or treatment for MM) will be measured as the total number of IP, OP, ED, and pharmacy claims that occurred over the follow-up period. Medical claims will only be counted once per day to estimate

visits, pharmacy claims will count all claims including multiple on the same day. Additionally, the total length of IP stays will be reported among patients with at least one IP visit. Given the recency of the study period, costs will not be adjusted for inflation. As the number of HCRU claims will vary by patient follow up time, results will also be reported as PPPM.

HCRU and associated costs will be measured across four different time periods. The first time period will be from 180 days prior to index date to one day prior to the index date, the second time period will be the index date until last recorded dose, the third time period will be during the step-up dosing period, the fourth time period will be the index date until discontinuation with an allowable 8-week gap of the index drug.

Patients will be censored at the earliest of death, next treatment (CAR-T, BsABs, bendamustine or belantamab), the end of continuous closed-claim coverage, or the latest data at the time of the specified analysis.

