9.7.7. Overall Survival and Time to Next Treatment

OS and TTNT/D will be assessed using unadjusted Kaplan-Meier methods. The median time to event in months will be reported along with the IQR. The 95% CIs for the median time to event will be calculated using log-log transformation. Results will be depicted graphically by Kaplan-Meier curves, and the percentage of patients who reached the outcome and censored patients will also be reported.

OS will be assessed as the time in months from index date to date of death. Patients without an event will be censored at the earliest of the end of continuous closed-claim coverage or the end of data.

TTNT/D will be assessed as the time in months from index date until switch a new treatment or death. Patients without an event will be censored at the earliest of the end of continuous closed-claim coverage, or the end of data.

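### Deaths are dated to the first of the month but used as exact dates, so early deaths get negative survival times and death-month claims are lost

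*Protocol*

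**What the plan says.** Protocol Section 9.4 describes the mortality field: "mortality is truncated to the year/month of death (YYYY-MM-01". Where sources disagree, "If multiple sources report different death dates for the same person, then the earlier date is taken". Both rules move a death earlier.

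The analysis sections then use this date directly:

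- Section 9.7.7, OS: "OS will be assessed as the time in months from index date to date of death".
- Section 9.7.7, TTNT/D: "TTNT/D will be assessed as the time in months from index date until switch a new treatment or death".
- Section 9.7.2, treatment exposure: "Patients will be censored at the earliest of death, next treatment (CAR-T, BsABs, bendamustine, or belantamab), the end of observability".
- Section 9.7.5, HCRU and cost: "Patients will be censored at the earliest of death, next treatment (CAR-T, BsABs, bendamustine or belantamab". Sections 9.7.3 (RAI) and 9.7.6 (adverse events) also censor at death.

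The other dates are held to the day. Section 9.7.4 converts days to months explicitly: "TTD will be assessed as the time in months (1 month = 30.4375 days) using Kaplan-Meier methods". The adverse event windows close 14 or 90 days after the last dose.

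No section assigns a day of death, deals with a recorded death before index, or says what happens to claims dated after the recorded death. The limitations in Section 9.9 do not mention the truncation. Section 9.8 commits the analysis to the protocol as written.

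**The concern.** An event date known only to the month is compared with start dates and claim dates known to the day, and it is always rounded down. Three things follow.

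- **Survival times.** Death times are shortened while index and censoring dates are not. A patient who dies in the calendar month of index, after an index date later than the 1st, has a recorded death before index.
- **Monthly rates.** HCRU and cost are primary (Objective 3) and are reported per patient per month. A recorded death on or before index leaves zero or negative person-time.
- **Safety.** Table 3 includes Grade 5 CRS and ICANS. If the claims for a fatal event fall in the death month after the 1st, they lie beyond the censoring date, so the rule tends to remove the events that those categories exist to count.

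**Working it through.** The protocol gives no survival figure, so there is none to reproduce. The inputs are the Section 9.4 truncation rule, the start of the index window (14 August 2023, Section 9.2), the planned end of data collection (20 November 2025, Section 6) as a stand-in for end of data, the month of 30.4375 days (Section 9.7.4) and the 56 patients with an elranatamab claim (Section 9.5, before eligibility criteria). Median OS is **assumed**, over a range.

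**1. Shift per death.** The shift is the true date minus the first of that month. Over all days in the window it runs from 0 to 30 days with a mean of 14.76 days; 14.76 / 30.4375 = 0.48 month. About 3% of deaths (those on the 1st) are not shifted.

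**2. Two worked cases.**

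- Index 20 March 2024, death 28 March 2024. True OS is +8 days; recorded OS is 1 March minus 20 March = -19 days.
- Index 10 January 2024, death 30 June 2024. True OS is 172 / 30.4375 = 5.65 months; recorded OS is 143 / 30.4375 = 4.70 months. Claims from 2 to 30 June fall after censoring.

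**3. Share of patients with a negative time.** With index days uniform over a month of m = 30.4375 days, the mean number of days left in the month, counting only index dates after the 1st, is (m - 1)(m - 2) / (2m) = 29.4375 × 28.4375 / 60.875 = 13.75. For exponential survival the daily hazard is ln 2 / (median × 30.4375). At a median of 12 months this is 0.693 / 365.25 = 0.00190, and 0.00190 × 13.75 = 2.6%. The same product gives 5.2%, 1.7% and 1.3% at medians of 6, 18 and 24.

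A simulation checks this: 1,000,000 patients per scenario, uniform index dates, exponential OS, administrative censoring on 20 November 2025, no disenrollment, and negative times kept as events.

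| Assumed median OS (months) | Negative OS, all patients | Expected among 56 | Chance of at least one in 56 | KM median, exact dates | KM median, truncated dates |
|---|---|---|---|---|---|
| 3 | 9.6% | 5.4 | 99.6% | 3.02 | 2.60 |
| 6 | 5.0% | 2.8 | 94% | 6.01 | 5.65 |
| 12 | 2.6% | 1.4 | 77% | 12.02 | 11.83 |
| 18 | 1.7% | 0.9 | 61% | 18.04 | 18.10 |
| 24 | 1.3% | 0.7 | 51% | 23.85 | 24.44 |

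**4. Where the damage sits.** For a death t days after index, the chance that it is recorded before index is about (m - t - 1) / m. Averaged over t = 1 to 14, this is 307.125 / 426.125 = 72%. Over t = 1 to 30 (zero at t = 30) it is 418.69 / 913.125 = 46%. This barely depends on the assumed median.

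**5. Direction of the median.** Up to 12 months the truncated median is short by 0.43, 0.36 and 0.20 month. At 18 and 24 months it is longer by 0.07 and 0.59. A death moved earlier is counted against a larger risk set, because patients censored between the recorded and true dates are still in it. Near the end of follow-up this can outweigh the shift.

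**6. Which windows are cut.** HCRU to discontinuation and the 14- and 90-day adverse event windows run past the last dose and are the most exposed. RAI, HCRU to the last dose, HCRU in step-up and TTD (measured to the last administration) are affected only if they reach into the death month. The 180-day baseline period is untouched.

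**The case against.** The truncation is a privacy constraint of the data source, and a day-of-death convention is often left to an analysis plan or programming specification, which is not shown here. Records with death before index would probably surface in quality control. OS and TTNT/D are exploratory, there are no formal comparisons, and Section 9.9 already warns of wide intervals. With 56 patients and a true median of 12 months, the KM median varies from about 7.8 to 19.2 months by sampling alone, so a shift of 0.2 to 0.4 month is minor.

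The point about the median stands, and the case does not rest on it. The rest does not remove the problem. The protocol does not leave the date open: it states the truncated value and names death as the event or censoring date in section after section. A rule improvised in quality control would not be prespecified.

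Three stronger readings are tempting, and the documents do not support them.

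- *OS and TTNT/D medians are always too short.* No individual death time is lengthened, but the table shows that the median can move up. In TTNT/D only the death component is affected.
- *The costliest month of life drops out of every window.* The documents give no cost by month, and several windows are usually unaffected.
- *Deaths after disenrollment count while disenrolled survivors are censored.* Section 9.7.7 says "Patients without an event will be censored at the earliest of the end of continuous closed-claim coverage or the end of data", and some death sources do not depend on enrollment. Read literally, with assumed annual disenrollment of 10%, 20% and 30%, a true median of 18 months would become about 17.0, 16.1 and 15.2. But the ordinary reading is no event during follow-up, and Section 9.2 ends general follow-up at the end of enrollment, while allowing outcome-specific rules. Under that reading the simulated median is 17.9 to 18.0. The wording needs a bound; it does not establish a bias.

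**Conclusion.** The concern holds. Followed as written, the protocol places deaths 0 to 30 days early (mean about 15 days). It gives negative OS and TTNT/D times and zero or negative monthly person-time to patients who die in the index month, about 5.0% to 1.3% of patients at assumed median OS of 6 to 24 months. It also drops claims after the first of the death month from the HCRU-to-discontinuation and post-dose adverse event windows. The number of claims, costs or fatal events lost cannot be computed from the documents.

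The effect on the KM median is modest: 0.2 to 0.4 month short at medians up to 12 months, and of either sign near the end of follow-up. The shares rest on exponential survival, uniform index dates and no disenrollment. The calendar arithmetic in steps 1 and 2 rests on none of these. Keeping the earlier of conflicting death dates pushes the same way by an amount that the documents do not allow one to estimate.

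**What to change.** In Sections 9.4 and 9.7:

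1. Impute the day of death as the later of day 15 of the death month and the last claim in that month, and never earlier than index + 1 day. Use this single date for OS, TTNT/D and person-time.
2. Count decedents' claims dated within the death month in the HCRU and adverse event windows, subject to each window's other end points. Because the imputed date is never before the last claim of that month, numerator and person-time agree.
3. Add a sensitivity analysis with the first and the last day of the month.
4. For OS, state that a death counts as an event only up to the bound that censors survivors: end of closed-claim coverage (to the month) or end of data. Follow-up to the end of mortality data may be a sensitivity analysis, not the primary rule. If only half of deaths after disenrollment were captured (assumed), it would turn a true median of 18 months into 18.9, 20.0 or 21.5 at 10%, 20% or 30% annual disenrollment.
5. List the truncation in Section 9.9.

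In the same simulation, day 15 with a floor of one day after index (without the last-claim element) gives KM medians of 2.99, 6.01, 11.99, 18.04 and 23.89 months, against 3.02, 6.01, 12.02, 18.04 and 23.85 with exact dates, and no negative times.

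The cost is a few lines of text and a rerun. The imputed day remains approximate, to about 15 days either way, and the sensitivity analysis shows how much that matters.

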9.5. Study Size

This retrospective cohort study will be largely descriptive in nature; sample size calculations are not directly applicable. At the time of the study, the dataset included over 700,000 patients with a claim for MM and 56 patients with a claim for elranatamab. The results of this study will be updated on a quarterly basis becomes available.

9.6. Data Management

Komodo Health receives raw data from several heterogeneous sources. Prior to the creation of any schemas, the data is first ingested and inspected to ensure its quality compared to previous deliveries from that source. If the data passes these initial tests, it is then mapped, cleaned, and reassembled. This process accomplishes the following tasks:

- **Mapping** individual fields from each of our sources are standardized to a uniform schema. Concordance validation is performed to ensure that mapping of individual source fields was performed accurately.

- **Cleansing** of mapped fields to a standard format in aggregate as much as possible. Examples of cleansing steps that do not need to be performed at the source-level include adjusting date fields to a consistent format, adjusting NDC fields to a standard of 11 characters, removing decimal points from ICD codes, and converting revenue codes to a 4-digit format.
- **Reassembly** of cleansed fields to account for source-specific cleaning and transformation steps in order to optimize downstream deduplication.

This produces a non-deduplicated, standardized representation of data from all sources. To ensure de-duplication, Komodo Health performs combinations of automated and manual data quality testing throughout the ingestion, transformation, data product development and maintenance life cycle. This testing is led by Komodo Health's Data Quality team, which is distinct from, and independent of the team that develops and maintains the data products. Komodo Health believes that this independent quality assurance process limits the potential for bias.

9.7. Data Analysis

This study will be largely descriptive in nature, and no formal statistical comparisons will be performed between groups. All characteristics and outcomes will be reported separately for each cohort. The prevalence and incidence, as well as the associated 95% CI for each AEs, will be estimated. Kaplan-Meier methods will be used to estimate the median time to event, including its 95% CIs.

9.7.1. Descriptive Analysis

Dichotomous and categorical variables will be summarized by the number and percentage of patients in each category. Continuous variables will be described using mean (SD), median (IQR), minimum, and maximum. If applicable, the frequency and percentage of patients with missing data for each variable will be described. Furthermore, baseline characteristics will be assessed among elranatamab or teclistamab patients with and without a laboratory observation.

9.7.2. Treatment Exposure Outcomes

Treatment exposure outcomes include RAI and time between administrations. The assessment periods shown in Table 4 are based on the elranatamab label instructions and will be used to measure treatment and dosing-related outcomes for patients receiving elranatamab.¹⁸ These periods are also provided in Figure 2.

[figure not shown]
Table 4. Dosing Schedule and Expected Administrations and Vial Size of Elranatamab

Dosing Schedule	Time Period	Expected Administrations	Vial Size

[figure not shown]
Step-Up	Index date - Day 8	3 during Step-Up	44mg/1.1mL
Maintenance Period 1	Day 9 - Day 168	1 per week	76mg/1.9mL
Maintenance Period 2	Day 169 – Censor	1 every two weeks	76mg/1.9mL

Figure 2. Dosing Schedule for Elranatamab and Teclistamab

Elranatamab label instructions

Teclistamab label instructions

The assessment periods shown in Table 5 are based on the teclistamab label instructions and will be used to measure treatment and dosing-related outcomes for patients receiving teclistamab.¹⁹ These periods are also provided in Figure 2.

Table 5. Dosing Schedule and Expected Administrations and Vial Size of Teclistamab

Dosing Schedule	Time Period	Expected Administrations	Vial Size
Step-Up	Index date - Day 7	3	30 mg/3mL
Maintenance Period	Day 8 - Censor	1 per week	153 mg/1.7mL

Dosing outcomes (reported vial size, average time between claims, and frequency of claims) will be assessed during the above time periods regardless of whether the number of administrations during the period matches the number indicated on the label instructions. Duration on treatment will be measured from the first administration to the last administration of the index drug.

Patients will be censored at the earliest of death, next treatment (CAR-T, BsABs, bendamustine, or belantamab), the end of observability, or the latest data at the time of the specified analysis.

9.7.3. Relative Administration Intensity

RAI will be calculated as the cumulative frequency of administration received over the expected number of administrations (see Table 4 and Table 5). There will be two RAI assessments with two different denominators; the first denominator will assess RAI as specified in the label (see Table 4 and Table 5), the second denominator will assume an administration every week after the Step-Up Period. The numerator will remain the same across the three different RAI assessments.

$$RAI = \frac{\text{Number of administrations received}}{\text{Number of expected administrations during the time period}}$$

Treatment exposure outcomes will be assessed across the different maintenance and step-up period. Patients will be censored at the earliest of death, the last administration of the index drug, or the latest data at the time of the specified analysis.

9.7.4. Time to Discontinuation

TTD will be assessed as the time in months (1 month = 30.4375 days) using Kaplan-Meier methods. Median time-to-event will be reported along with the IQR. The 95% CIs for the median time-to-event will be calculated using log-log transformation. Results will be depicted graphically by Kaplan-Meier curves.

Patients who do not have a recorded discontinuation event or death will be censored on the earliest of the end of continuous closed-claim coverage or the end of data.

The percentage of patients who reached the outcome, as well as the percentage of censored patients, will be reported.

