2.0	31 July 2025	Substantial	9.7.1	Additional lab variable subgroup in the baseline characteristics	This subgroup will help contextualize any difference with respect to lab availability
2.0	31 July 2025	Substantial	9.7.2: Figure 2	The study figure was updated The time period of assessment for duration on treatment and censoring reasons as clarified.	To clarify the exact end dates for each dosing period, reflecting ELREXFIO label. The set end date was removed and replaced with flexible language reflecting the amendment to conduct quarterly updates.
2.0	31 July 2025	Substantial	9.7.3	RAI assessment added. Censoring criteria for RAI was updated to include the last administration of the index treatment. Study end date replaced with flexible language	The addition of this analysis better help contextualize the “upper” bound of RAI. Last administration of the index treatment was included as a censoring criterion as many patients

					have long periods of no treatment from their last administration to the censor date. RAI estimates seemed to be underestimated due to this factor.
2.0	31 July 2025	Substantial	9.7.4	Removal of the phrase stating "If follow-up time is adequate" Study end date replaced with flexible language	Patients will be included in the TTD assessment regardless of duration of follow-up. The set end date was removed and replaced with flexible language reflecting the amendment to conduct quarterly updates.
2.0	31 July 2025	Substantial	9.7.5	A sentence to clarify pharmacy claim capture for HCRU was included. A sentence rationalizing the usages of PPPM estimates was included. An additional time period for HCRU	The additional sentences were for clarification. The new time of assessment was a request based on interest in measuring HCRU during the step-up period.

				assessment was included. Study end date replaced with flexible language	The set end date was removed and replaced with flexible language reflecting the amendment to conduct quarterly updates.
2.0	31 July 2025	Substantial	9.7.5	Study end date replaced with flexible language	The set end date was removed and replaced with flexible language reflecting the amendment to conduct quarterly updates.
2.0	31 July 2025	Substantial	9.7.6	Study end date replaced with flexible language	The set end date was removed and replaced with flexible language reflecting the amendment to conduct quarterly updates.

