3	TTD	Time in months from first administration until last administration prior to treatment discontinuation (continuous). Treatment discontinuation is defined as an 8-week gap in elranatamab (or for the exploratory analysis, teclistamab therapy), next treatment after index treatment (CAR-T, BsABs, bendamustine or belantamab), or death.	Index date to the end of follow-up. Follow-up will be defined based on the censoring criteria described in Section 9.7.4
Health care resource utilization and costs			
4	All-cause IP visits	Medical claim for IP (non-ED) visit (dichotomous)	180 days prior to index date to 1 day prior to index date
		Number of IP (non-ED) visits (continuous)	Step-Up Dosing Period Index date to end of follow-up. Follow-up will be defined two ways to account for gaps in elranatamab use. See Section 9.7.5 for censoring criteria
4	IP visits from the IP table	Medical claim for IP (non-ED) visit sourced from the IP table (dichotomous)	180 days prior to index date to 1 day prior to index date
		Number of IP (non-ED) visits sourced from the IP table (continuous)	Step-Up Dosing Period Index date to end of follow-up. Follow-up will be defined two ways to account for gaps in elranatamab use. See Section 9.7.5 for censoring criteria
4	IP visits from the Non-IP table	Medical claim for IP (non-ED) visit sourced from the Non-IP table where place of service indicates an IP setting (dichotomous)	180 days prior to index date to 1 day prior to index date

		Number of IP (non-ED) visits sourced from the IP table place of service indicates an IP setting (continuous)	Step-Up Dosing Period Index date to end of follow-up. Follow-up will be defined two ways to account for gaps in elranatamab use. See Section 9.7.5 for censoring criteria
4	All-cause OP visits	Medical claim for non-IP/non-ED visit (dichotomous)	180 days prior to index date to 1 day prior to index date
		Number of non-IP/non-ED visits (continuous)	Step-Up Dosing Period Index date to end of follow-up. Follow-up will be defined two ways to account for gaps in elranatamab use. See Section 9.7.5 for censoring criteria
4	All-cause ED visits	Medical claim for ED visit (dichotomous)	180 days prior to index date to 1 day prior to index date
		Number of ED visits (continuous)	Step-Up Dosing Period Index date to end of follow-up. Follow-up will be defined two ways to account for gaps in elranatamab use. See Section 9.7.5 for censoring criteria
4	All-cause pharmacy claims	Pharmacy claim (dichotomous)	

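### Time to discontinuation cannot register a gap-only stop in the last 56 days before censoring, so Kaplan-Meier TTD is biased upward, strongly at early data cuts and modestly at the final one

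*Protocol*

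**What the plan says.** Protocol Section 9.3, Table 3, defines TTD as "Time in months from first administration until last administration prior to treatment discontinuation (continuous". An event therefore carries the date of the last dose, not the date on which the stop becomes visible. On what counts as a stop: "Treatment discontinuation is defined as an 8-week gap in elranatamab (or for the exploratory analysis, teclistamab therapy), next treatment after index treatment" (CAR-T, bispecific antibodies, bendamustine or belantamab), or death. For follow-up the table defers to one place: "Follow-up will be defined based on the censoring criteria described in Section 9.7.4".

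Section 9.7.4 specifies the estimator, "TTD will be assessed as the time in months (1 month = 30.4375 days) using Kaplan-Meier methods", and the censoring rule: "Patients who do not have a recorded discontinuation event or death will be censored on the earliest of the end of continuous closed-claim coverage", with the data cut-off as the alternative date.

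The V2.0 amendment table (Section 5) removed an adequacy-of-follow-up condition from TTD, with the reason "Patients will be included in the TTD assessment regardless of duration of follow-up". In the same amendment, censoring for relative administration intensity (RAI) was moved to the last administration because many patients "have long periods of no treatment from their last administration to the censor date". TTD censoring was not changed in that way.

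**The concern.** The event date and the censoring date do not fit together. A gap event is placed at the last dose but needs 56 further observed days to be recognised. A patient who stopped 30 days before the end of data, and has neither died nor switched, is censored at the end of data, 30 days after the true stop. A patient with under 56 days of follow-up can never show a gap event.

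Kaplan-Meier thus counts time at risk in which one type of event cannot be recorded, which pushes the curve and its median up. The affected share of follow-up shrinks as data mature. Section 6 plans interim and full results, four refreshes and a final report, so reported TTD would move between cuts with no change in how long patients stay on treatment.

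**Working it through.** The protocol states no TTD figure, event count or expected median, so there is nothing to reproduce. The check has two parts.

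**1. Direction, by algebra.** Let T be the time to last dose, with density f, survivor function S and hazard h. Let C be the time to end of coverage or data, and G(t) = P(C ≥ t). Take gap-only stops.

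- Events recorded at t: f(t) × G(t + 56), because 56 further days must be seen.
- Risk set at t: at least S(t) × G(t), plus unconfirmed stoppers still carried to C.
- Estimated hazard: at most h(t) × G(t + 56) / G(t), which is below h(t).

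With uniform entry over H days, G(t + 56)/G(t) = (H − t − 56)/(H − t). At t = 183 days (6 months):

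- H = 365: 126/182 = 0.69.
- H = 829 (14 August 2023 to 20 November 2025): 590/646 = 0.91.

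At 6 months, then, the hazard of a gap-only stop is understated by at least 31% in a 12-month-old cohort and by at least 9% at the final cut.

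Censoring unconfirmed patients at their last dose removes only the extra stoppers from the risk set. The factor G(t + 56)/G(t) stays, so most of the bias stays.

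**2. Size, by simulation** (400,000 patients per scenario).

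From the protocol: index dates from 14 August 2023, end of data collection 20 November 2025, 56-day gap, 30.4375 days per month, and dosing weekly to day 168 then every two weeks.

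Assumed: exponential time on treatment, uniform entry, and 0, 30 or 60% of stops made visible by death or next treatment. The earlier cut dates are also assumed.

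Median TTD in months, with last doses on the dosing grid and visible stops seen within 8 weeks; ranges run over 0 to 60% visible:

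| End of data (days from 14 Aug 2023) | True median | As written | Follow-up closed 56 days early |
|---|---|---|---|
| 24 Apr 2024 (254) | 3.0 | 3.9–4.6 | 3.0 |
| | 6.0 | not reached | 5.5–6.0 |
| 15 Nov 2024 (459) | 3.0 | 3.2–3.5 | 3.0 |
| | 6.0 | 6.4–6.9 | 6.0 |
| | 12.0 | not reached | 11.5–12.0 |
| 20 Nov 2025 (829) | 3.0 | 3.0–3.2 | 2.8–3.0 |
| | 6.0 | 6.0–6.4 | 6.0 |
| | 12.0 | 12.4–12.9 | 12.0 |

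Across these scenarios, 5 to 26% of censored patients had already stopped and missed a scheduled dose.

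Without the dosing grid, for a true median of 6.0:

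- Follow-up uniform over 0–12 months: 8.4 with no stops visible early and 7.3 with 30% visible at once (6.7 with 60%).
- 0–18 months, none visible early: 7.0. Censoring at last administration gives 6.9.
- About 27 months (829 days), none visible early: 6.55, and 6.55/6.00 − 1 = 9%. With 60% visible at once: 6.2.

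**A trap in the repair.** If closed coverage ends at death and the horizon is coverage end minus 56 days, every patient who dies within 8 weeks of the last dose is censored instead of counted. With 30% of stops being such deaths, a true 6.0 becomes 8.3, so the horizon must not be set by a death.

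**The case against.** The strongest reply concerns size. V2.0 is dated 31 July 2025, so only refreshes 3 and 4 and the final report lie ahead, and the large figures belong to cuts already past. At the final cut the shift is 0 to about 0.6 months on a 6-month median. Sampling error is larger: with a true median of 6.0 and 27 months of uniform accrual, the 95% sampling range of the median is about 4.0–9.1 at n = 56 (the count the protocol gives for April 2024) and 5.0–7.1 at an assumed n = 300. Section 9.9 itself warns of wide intervals. This stands as a limit on practical weight. It does not remove the bias, which more patients will not average away. Rising uptake or early loss of coverage would shorten follow-up and enlarge it.

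Three stronger readings are tempting, and the documents support none of them.

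- **That reported TTD is overstated on balance.** A patient who pauses for more than 8 weeks and resumes, or whose doses are missing from claims, is counted as an early stop, which shortens TTD. The simulation contains no such patients. It shows an upward component, not the net direction.
- **That the rule favours elranatamab over teclistamab.** Both cohorts share the index window and the censoring rule, and Section 9.7 plans no formal comparison. Their follow-up may differ, but the protocol does not say so.
- **That most events are lost in the window.** Death and next treatment still count there, and the protocol gives no event mix.

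**Conclusion.** The point holds for gap-only stops. Table 3 and Section 9.7.4 together fix a rule under which such stops in the 56 days before censoring are carried as time on treatment, and nothing elsewhere in the protocol corrects it. The mechanism and its upward direction are certain. The size is conditional on exponential stopping, uniform entry and the assumed share of stops visible through death or switch.

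For a true median of 6 months it is about 7.3 to 8.4 months with 0–12 months of follow-up, and 6.0 to 6.6 (0 to about 9%) at the final cut. The early figures should not be read across to the final report. The main practical consequences are drift in TTD between refreshes and a modest upward component in the final estimate. The rule should be changed, and the change is small.

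**What to change.** Amend Section 9.7.4 to say:

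- The TTD horizon for each patient is 56 days before the earlier of the end of data or the end of closed coverage for reasons other than death.
- A last dose on or before the horizon is an event at that dose if a gap, listed next treatment or death followed. The final 56 days serve only to confirm this.
- Patients with a dose after the horizon are censored at the horizon.
- A coverage end caused by death does not set the horizon. For patients who die, use the end of data, or the coverage end that would otherwise apply, so that deaths soon after the last dose remain events.
- The rule as now written is reported as a sensitivity analysis.

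Censoring at last administration should not serve as the sensitivity analysis. It keeps nearly all the bias (6.9 against 7.0 months), and its agreement with the current rule would look like robustness. No change to the resource-use windows in Section 9.7.5 is proposed. They have their own censoring rule, and no error in them has been shown here.

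Cost: no new data. Up to 56 days of follow-up per patient are given up, and patients with under 56 days of potential follow-up contribute nothing to the main TTD estimate. That departs from the V2.0 decision to include everyone regardless of follow-up, and the amendment should say so. The sensitivity analysis keeps those patients.
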